Interventions and Treatment Fidelity Methods: The B-SWELL intervention will follow procedures such as those proposed in Figure 1 and will be refined prior to trial based on feedback from the community collaborators and expert ratings (Aim1). Participants will be randomized to either the B-SWELL or WE groups. Both groups will be introduced to the LS7 materials. The B-SWELL will receive additional instruction about stress. B-SWELL and WE group sessions will occur on different dates and times and, participants will be asked not to share experiences with women outside of their assigned group. Participants will also be asked to secure private location when attending the virtual sessions to ensure privacy and confidentiality. Treatment fidelity of both groups will be monitored using Borrelli's Treatment Fidelity Checklist (Design, Training, Delivery, Receipt, Enactment). Facilitators of the intervention and control groups will be trained prior to the start of the trials.. Zoom meetings will be audio taped for quality assurance.

Data Collection Procedures: Aim 2. Data collection will occur at baseline, 8 weeks, and 12 weeks. Baseline data will be collected from B-SWELL and WE participants using telephone interviews conducted by trained, blinded research assistants. Data collection at 8 and 12 weeks may be collected via phone interview or through a REDCap link on the B-SWELL study tablets provided to B-SWELL and WE participant. Completion of the surveys (interview or via REDCap link) is expected to last 30-45 minutes for each timepoint. Instruments are listed in Table 5. 3.4.d.

Randomization Procedures: Following baseline data collection, participants will be randomized to either the B-SWELL or WE group using 1:1 block randomization to promote equal group sizes. The randomization allocation sequence will be blinded to data collectors to avoid bias during follow-up data collection telephone interviews. Following randomization, the PI or research assistant will notify the participant of their group assignment and upcoming group meetings. Treatment fidelity will be monitored using the Borrelli's Treatment Fidelity Checklist (Design, Training, Delivery, Receipt, Enactment).

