Protections against risk. Participants may choose not to answer items during interviews or participate in portions of the intervention program with which they are uncomfortable. In the unlikely event that a participant appears to be distressed, she will be referred to appropriate resources or be given the telephone number for the national Suicide [contact]; [name]) if appropriate. The PI will inform the IRB of any adverse events and/or any amendments to the protocol. Training for data collectors also will include how to respond to any potential adverse events experienced by participants, such as suicidal tendencies or severe depression. Participants with these types of problems will be given information about how to seek help and will be encouraged to inquire whether medication and/or psychological counseling would be helpful. In the event of suicidal thoughts, the PI or research staff may contact a health care provider on the participant's behalf so that they can contact the participant directly to determine if treatment is necessary.

To avoid loss of confidentiality during the online Zoom sessions, participants will be asked to find a private location from which to attend the online Zoom sessions. Additionally, participants will be required to attend Zoom sessions with video and will be asked to keep session discussions and activities private.

Only authorized study personnel will have access during the Zoom sessions, Zoom audiotapes or transcriptions, REDCap data, database, or contact information for study participants and expert panel members. For data analysis, study ID numbers will be generated to protect the identity of the participants in the final data set. Participants will not be identified in any way in reports or manuscripts from the study. Data from surveys will input directly into a REDCap database either manually or via the link on the study tablets. REDCap is backed up nightly by the university. Only authorized study personnel will have access to REDCap. Any calls to participants will be made to a telephone number provided by the participant at a time that is convenient for the

participant. Research staff will make calls from a private location in order to protect confidentiality. Informed consent forms and contact information from participants will be stored separately in a locked file cabinet to protect confidentiality.

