Secondary Outcome	Perceived General Health: Uses the general health perception item from the Short Form Health Survey (SF36). Health rated as 'excellent', 'very good', 'good', 'fair' and 'poor'. ⁷¹	2	Х	X	Х
Secondary Outcome	Patient Health Questionnaire (PHQ-9): A diagnostic instrument for depressive symptoms. Scores each of the 9 DSM-IV criteria as '0' (not at all) to '3' (nearly every day). ⁷²	5	Х	Х	Х
Program Evaluation	Satisfaction (Adapted from Satisfaction questionnaire): Measures usefulness, ease of use, and acceptability ratings.(Bakas et al., 2009)	10			Х
Technology Evaluation	Satisfaction (Adapted from Satisfaction questionnaire): Measures usefulness, ease of use, and acceptability ratings.(Bakas et al., 2009)	5			Х
Total Minutes	Total data collection minutes each visit	40 min	30 min	25 min	35 min

6.4 What data will be collected during the study and how that data will be obtained?

Rating surveys, self-report survey data, and satisfaction ratings will be gathered from the expert panel and participants (Aims 1 & 2) and entered directly into a REDCap database via laptop computer or REDCap survey link. Intake data will be labeled with study ID numbers and stored separately. Names, contact information, or any other identifiers will be stored separately from all data that is collected. Access to the database, contact information, or links between study ID numbers and participants enrolled in the study will be limited to the investigators. Participants will not be identified in reports or manuscripts from the study. All paper forms and study materials will be stored in locked file cabinets accessible only to authorized study personnel. All computers, servers, and electronic files used in the study will be password protected and accessible only to authorized study personnel. Authorized study personnel will include the investigators and research staff involved in the study.

6.5 If there are plans for long-term follow-up, what data will be collected during this period.

A third and final data collection time point will occur 4 weeks after the completion of the intervention (12 weeks).

6.6 For Humanitarian Use Device (HUD) uses provide a description of the device, a summary of how you propose to use the device, including a description of any screening procedures, the HUD procedure, and any patient follow-up visits, tests or procedures.

N/A

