The Zoom platform has been approved by the UC Department of Research. Zoom provides advanced security and infrastructure to provide security during online activities. Administrators have the ability to perform secure log-ins, start a secured meetings with password, and schedule secured meetings with password. Secure meeting capabilities include the following:

- Role-based user security (i.e. waiting room, lock a meeting, end a meeting, expel a participant)
- Host and client authenticated meeting
- Open or password protected meeting
- Edit or delete meeting
- Host controlled joining meeting
- In-meeting security (i.e. all data is encoded)
- Authentication

The account administrator (study PI) will have the following security capabilities:

- Secure login options using standard username and password or SAML SSO
- Add user and admin to account
- Delete user from account Security Guide Zoom Video Communications, Inc. July 2020
- Manage account dashboard and cloud recordings
- 17.3 Describe any procedures that will be used for quality control of collected data.

For Aim 1, ratings will be obtained using survey tools adapted from a validated satisfaction questionnaire. For Aim 2, data will be collected using validated survey tools. In addition, data will be collected via phone to decrease the risk for missing data. Data collected via the B-SWELL study tablet will be linked directly to the REDCap. REDCap will be used to organize, store, and secure data. Only trained research personnel will handle the data and have access to REDCap.

17.4 Describe how data or specimens will be handled study-wide:

Rating surveys, self-report survey data, and satisfaction ratings will be gathered from the expert panel and participants (Aims 1 & 2) and entered directly into a REDCap database via laptop computer or REDCap survey link (for experts). Intake data will be labeled with study ID numbers and stored separately. Names, contact information, or any other identifiers will be stored separately from all data that is collected. Access to the

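### The PHQ-9 at 8 and 12 weeks may be self-completed by REDCap link, but the protocol writes no step for noticing a worrying answer sent that way

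*Combined protocol and SAP*

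**What the plan says.** **Mode of collection.** Baseline is by telephone interview (section 6.2.2, Data Collection Procedures: Aim 2). For the later visits the same paragraph says: "Data collection at 8 and 12 weeks may be collected via phone interview or through a REDCap link on the B-SWELL study tablets".

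**What is collected.** The survey chart in section 6.3 marks the PHQ-9 at baseline, 8 weeks and 12 weeks, and describes it as "A diagnostic instrument for depressive symptoms. Scores each of the 9 DSM-IV criteria". The chart gives the 0-to-3 item scoring but no score or item that calls for action.

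**Where link answers go.** Section 6.3 says: "Data from surveys will input directly into a REDCap database either manually or via the link on the study tablets". Section 17.3 repeats the route: "Data collected via the B-SWELL study tablet will be linked directly to the REDCap".

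**What protects a distressed woman.** Section 6.3, Protections against risk, says: "In the unlikely event that a participant appears to be distressed, she will be referred to appropriate resources". It provides for training data collectors to respond to suicidality or severe depression, and adds: "Participants with these types of problems will be given information about how to seek help". If suicidal thoughts arise, the principal investigator or research staff may contact a health care provider. Section 25.1, Medical and Psychiatric Resources, repeats this text and adds referral to UC Health.

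**The concern.** The protocol foresees suicidality and severe depression, and its promise of help is not limited to women reached by phone. In a phone interview, a trained person hears the answer as it is given. When the link is used, the answer enters a database, and no one is assigned to read it within any stated time. Two women giving the same answer could be treated differently because of the route they used, not because of their need.

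The entry exclusions for suicidal tendencies and severe untreated depression (sections 6.2.2 and 10.2) make such answers less likely. They are applied at screening, however, and cannot cover symptoms first reported at 8 or 12 weeks.

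**Working it through.** The plan states no figure on this point. The check is a reading of the relevant sections, followed by a count of the forms exposed.

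**Step 1: sort the written provisions into noticing and responding.**

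| Provision | Section | Notices a link answer? | Responds once known? |
|---|---|---|---|
| Referral or crisis-line number if she appears distressed | 6.3, 25.1 | No | Yes |
| Training of data collectors | 6.3, 25.1 | No; none is present | Yes |
| Information on seeking help | 6.3, 25.1 | No | Yes |
| Contact with a health care provider | 6.3, 25.1 | No | Yes |
| UC Health evaluation | 25.1 | No | Yes |
| Quality control of data | 17.3 | No; covers tools, missing data and access | No |
| Safety monitoring | 18.0 | Marked not applicable | Not applicable |
| Monthly reviews and weekly meetings | 25.1, Verification | No; cover procedures and staff adherence | Issues in general |

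Every response step waits on someone noticing. For a form sent by link, no section supplies a reader, an alert, an action threshold or a time limit.

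**Step 2: compare the statements on mode.** Section 6.2.2 speaks of telephone interviews at all three time points in its program-evaluation paragraph, but allows the link in its data-collection paragraph. Section 6.3 places the sensitive items in phone interviews. Section 15.1 says collection is by phone at every time point. The risk text thus describes a procedure with an interviewer always present, while the procedures permit one without.

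**Step 3: count the forms.** Inputs: 50 women (section 12.1); three PHQ-9 administrations, with the link allowed at two (section 6.3 chart and section 6.2.2).

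- Planned forms: 50 × 3 = 150.
- Forms for which the link is allowed: 50 × 2 = 100, and 100/150 = 66.7%.
- Forms with no interviewer = 100 × uptake. Uptake is not in the documents, so the values below are assumptions.

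| Assumed link uptake | Forms without interviewer | Share of 150 |
|---|---|---|
| 0% | 0 | 0% |
| 10% | 10 | 6.7% |
| 50% | 50 | 33.3% |
| 100% | 100 | 66.7% |

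Sections 12.2 and 17.1 plan to oversample at baseline against dropout. Each additional woman adds up to two link-eligible forms, so 100 is not a strict ceiling.

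**Step 4: cost of giving the PHQ-9 by phone instead.** The chart allots 5 minutes to the PHQ-9. Extra time = link forms replaced × 5 minutes:

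- 10% uptake: 10 × 5 = 50 min = 0.8 h
- 50% uptake: 50 × 5 = 250 min = 4.2 h
- 100% uptake: 100 × 5 = 500 min = 8.3 h

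If scheduling and repeat calls add an assumed 10 to 20 minutes, each form takes 15 to 25 minutes. The totals become 2.5 to 4.2 h at 10% uptake and 25 to 41.7 h at 100%.

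**The case against.** The strongest reply is that the response steps do not depend on mode. Anyone on the team who learns of suicidal thoughts, by whatever route, may act on them under sections 6.3 and 25.1. That is right. A reader might infer that a worrying link answer triggers nothing at all; the documents do not support this, because response is provided for. What is missing is the step by which someone learns of the answer.

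Second, the phone route is not fully specified either. No PHQ-9 item, score or time limit is written for it, and provider contact is optional. This also stands. The difference between the routes is the presence of a trained listener, so a threshold should cover both.

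Third, a reader might infer from section 6.4 that only an investigator could respond, since it says: "Access to the database, contact information, or links between study ID numbers and participants enrolled in the study will be limited to the investigators". Sections 6.3, 17.4 and 19.3 weaken that reading. They give database and contact access to authorized personnel, a group defined to include research staff, and section 6.3 lets research staff contact a provider. The responder needs to be able to identify the woman, but need not be an investigator.

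Fourth, week 12 might seem a special case, because "A third and final data collection time point will occur 4 weeks after the completion of the intervention". The contrast is thin: the 8-week survey falls as the sessions are ending too, so contact through sessions hardly separates the two visits.

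Finally, this is a minimal-risk pilot with relevant exclusions. Alert settings could sit in an operations manual, and help text could appear in the attached surveys or consent material, none of which was available. These points limit the severity. They do not supply the missing step in a protocol that already writes its distress procedures in some detail.

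**Conclusion.** The point holds as a gap in detection. Followed as written, the protocol allows an answer indicating suicidality or severe depression to arrive by link and go unread, while the same answer by phone reaches a trained person. It affects between 0 and about 100 of 150 planned PHQ-9 forms, depending on an uptake the documents do not give, and more with oversampling.

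This rests on two assumptions: that the link option in section 6.2.2 is in force despite the phone-only wording elsewhere, and that no alert or help text is set out in material not seen. It does not show that any woman would come to harm. No rate of worrying answers is given, and none is assumed. Nor does it bear on the endpoints, power or analysis.

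The sponsor should correct it because the safety gain is specific and cheap. Confidence is medium, given the unseen attachments.

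**What to change.** In section 6.3, Protections against risk, and its repeat in section 25.1:

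1. Set one PHQ-9 item or score threshold that calls for action, chosen by the sponsor, applying to phone and link forms alike and in both arms.
2. For link forms, add an automatic REDCap alert at that threshold. Send it to a designated investigator or authorized staff member who can identify the participant and is not a blinded data collector.
3. State a call-back time, and show help-line text when the form is submitted.
4. Bring the phone-only wording in sections 6.2.2, 6.3 and 15.1 into line with the link option.

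The cost is a small REDCap set-up task, a paragraph of wording, and an existing investigator or staff member available to respond. The team already programs the tablets (section 6.3) and has REDCap survey support (section 25.1). Sample size and analysis do not change.

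Alternative: give the PHQ-9 by phone at 8 and 12 weeks through the blinded data collectors and leave the other surveys on the link. The extra staff time is proportional to the link use replaced: at most about 8 hours for the questionnaire itself with 50 women, plus contact time as worked above. Women who are hard to reach by phone could have missing PHQ-9 data. The threshold in item 1 would still be needed.

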7.0 Data and Specimen Banking*

7.1 If data or specimens will be banked for future use, describe where the specimens will be stored, how long they will be stored, how the specimens will be accessed, and who will have access to the specimens.

N/A

7.2 List the data to be stored or associated with each specimen.

N/A

7.3 Describe the procedures to release data or specimens, including: *the process to request a release, approvals required for release, who can obtain data or specimens, and the data to be provided with specimens.*

N/A

8.0 Sharing of Results with Subjects*

8.1 Describe whether results will be shared with subjects or others and if so, describe how the results will be shared.

We anticipate that there will be manuscripts, not only from the findings addressing Specific Aims 1 and 2, but also from secondary analyses from data generated from this study. We will disseminate results from Specific Aims 1 and 2, as well as results from secondary analyses, in peer-reviewed journals. We will also make the data available to others. Data will be shared with undergraduate honors students, MSN students, DNP students, PhD students, post-doctoral students, and interested faculty members at the University of Cincinnati, College of Nursing, and other institutions. Special measures will be taken to ensure that participants are not identifiable by any data that are shared. Close collaboration between the PI and her research team will be necessary for the use of shared data.

This is a community-based participatory research plan and dissemination efforts will include community presentations to share the findings of the research and discuss its relevance and usefulness to the community. Measures will be taken to de-identify any data that is shared. Feedback and ideas from the community will be taken into consideration with future iterations of this research and larger clinical trials based upon the findings.

This study will be registered and study results will be submitted to ClinicalTrials.gov in accordance with the NIH policy. Informed consent documents will include statements relating to the posting of clinical trial information at ClinicalTrials.gov.

9.0 Study Timelines*

The duration for individual participation in the study is 12 weeks. The duration anticipated to enroll all study participants is 12 months. The estimated date for the investigators to complete primary analysis is April 2022. Please see the study timeline below:

Grant Timeline	Year 1			Year 2				Year 3				
Month	3	6	9	12	15	18	21	24	27	30	33	36
Mentoring												
Didactic Coursework												
Workshops and conferences												
· ·												
IRB approval process												

Advisory board meetings - guarterly						
Aim 1: Develop the B-						
SWELL components						
Aim 1: Obtain ratings of B-						
SWELL components						
Aim 1: Data Analysis						
Aim 1: Refine B-SWELL						
components						
Aim 2: Recruitment						
Aim 2: Data collection						
Aim 2: Data analysis						
Aim 1&2: Dissemination						
R01 Grant writing						
K01 progress reports						

10.0 Inclusion and Exclusion Criteria*

10.1 Describe how individuals will be screened for eligibility.

Recruitment will involve use of fliers, referral, snowballing, and purposeful sampling in targeted communities (Aim 1 & 2). Potential participants will express their interest by contacting the research team. Screenings will take place via phone. If a potential participant meets the study requirements, and agrees to the terms of the study, they will be randomized to either the intervention (B-SWELL) or control (WE) group (Aim 2).

10.2 Describe the criteria that define who will be included or excluded in your final study sample.

For Aim 2, inclusion criteria include self-identification as Black or African-American, between the ages of 40 and 64, fluent in the English language, ability to hear and speak well enough to engage in everyday conversation, an email address, access to a telephone and WIFI, and willingness to participate. Exclusion criteria include recent immigration to the U.S., prisoner or on house arrest, pregnant, terminal illness (i.e., late stage cancer, end-of-life condition, renal failure requiring dialysis), history of Alzheimer's, dementia, or severe mental illness (i.e., suicidal tendencies, schizophrenia, or severe untreated depression), or any other major health conditions or disabilities (i.e. visual impairment, blindness, deafness) prohibiting safe or full participation in the program.

Indicate specifically whether you will include or exclude each of the following special populations:

• Adults unable to consent

Adults who are unable to consent will be excluded from this research study because this intervention focuses on increasing self-efficacy and one's ability to make decisions about lifestyle changes to improve health. An inability to consent for one's self speaks to agency. It is a contraindication for this study and implies that someone else may be deciding for the participant.

• Individuals who are not yet adults (infants, children, teenagers) This research is targeted specifically to midlife Black women. Children and adolescents will not be recruited.

Pregnant women are also excluded from this study. The study focuses on healthy lifestyle behavior and stress reduction; activities which should be beneficial to pregnant women. However, each pregnancy is unique and would require additional supervision. Safety measures for pregnant women are NOT included in the study procedures

Prisoners

Prisoners are excluded from this study as it is community-based research and requires participants to freely participate in virtual group activities, receive B-SWELL study documents in the mail, and have access to WIFI and a private location for group sessions.

